after induction of general anesthesia. Post TAVR RV assessment is done in the same way as baseline RV function assessment.

2. **Compare 3D RV EF between SAVR, mini AVR, TAVR.**

See Table below for the timing of assessment

	SAVR	Mini AVR	TAVR
Baseline RV (T#1)	Post induction		
Post valve deployment RV (T#2)	Post CPB		Post valve deployment
Post chest closure RV (T#3)	Post chest closure or before extubation		

B. Background and Significance

The importance of postoperative RV function after cardiac surgery has been recognized for more than 30 years, but its assessment has been challenging due to the unique anatomy, physiology, and its position. The RV is pyramid shape, its contraction consists mostly of longitudinal movement, and is less accessible due to its retrosternal position. Thus, RV function assessment has been comprehensive utilizing RV size, RIMP, RV FAC, S', TAPSE, surgeons' "eyeball" impression. With emergence of 3D echocardiography technology, 3D-derived RV EF is the most accurate echocardiographic measure of global RV function¹ Previous study^{3,4} has shown that RV function is more reduced in SAVR than TAVR however their RV assessment was mostly with 2-dimensional echocardiography. This study will be the first study to utilize 3D echocardiography for RV function assessment for SAVR, mini AVR, and TAVR.

C. Preliminary Studies/Progress Report

N/A

D. Research Design and Methods

Design: Prospective clinical trial at single-center tertiary academic hospital.

Participants: Aortic valve surgery patients

Arm 1 (SAVR)

Arm 2 (mini AVR)

Arm 3: (TAVR)

Primary outcome: 3D RV EF

Secondary outcome: Traditional RV function indices (RVFAC and TAPSE)

[figure not shown]
Anesthesia methods: general anesthesia with endotracheal intubation, arterial line, central venous line, pulmonary artery catheter (not for TAVR), TEE.

Anesthesia will be general anesthesia with endotracheal tube, pre-induction arterial line, central venous line, pulmonary arterial catheter (not for TAVR), and TEE; all of which are within standard care, and nothing specific to this study. Choice of the medication including inotropes and vasopressors, and intervention such as transfusion and fluid management will be at each anesthesiologist's discretion.

Measurements:

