Summary statistics will be reported for demographic and clinical data for each group. Similarly, variables are presented as mean \pm SD and median (IQR), when indicated. Categorical data are presented as frequencies and percentages according to the group. Demographic data will be analyzed using the independent t-test, and the Mann–Whitney U test will be used for nominal variables. RV echocardiographic indices will be analyzed using the Mann–Whitney U test (2 groups) or the analysis of covariance (ANCOVA) and pos-hoc pairwise comparisons with Bonferroni correction. For ANCOVA of % change (Timing #3 from #1) in RV indices, covariates included age, gender, norepinephrine equivalent (NE equiv) at Timing #3, CVP at Timing #1, and each RV index at the baseline (Timing #1). Univariate or multivariable logistic regression models were used to assess the association between each echocardiographic index and in-hospital MACCEs. Correlations between continuous variables will be assessed using Pearson's or Spearman's rank correlation tests. Statistical significance is set at $p < 0.05$. All statistical analyses are performed using R version 4.5.1 (The R Foundation for Statistical Computing).

Power analysis

Changes in RV echocardiographic measurements were used to calculate the required sample size, based on a study by Kempny et al.[4] Kempny et al. reported %change of right ventricular strain of - 25.2 (SAVR) and - 20.0 (TAVR) before and after the

procedure, respectively. With the criterion for significance (alpha) set at 0.05 and 80% power for a Mann–Whitney U test, we obtained a sample size of 22 patients per group. The rationale for using RV strain for power analysis is as follows; Sample size calculations for RV strain, RVFAC, and TAPSE provided 22, 7, and 15, respectively. Thus, we decided to use the strictest sample size calculation.

F. Gender/Minority/Pediatric Inclusion for Research

Adult patients over 18 years old are included. Any gender and race patients are included.

G. Human Subjects

1. Inclusion criteria: Adult patients over 18 years old who have mitral valve procedures
Exclusion criteria: patients' refusal, suboptimal echocardiography data
2. Sources of research material in the form of specimens, records or data.
Echocardiography data, medical information in EPIC
3. Plans for recruitment and consent procedures to be followed.
Phone consent will be done in preoperative or actual consent will be obtained in preoperative holding area.

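### Bonferroni on the three pairwise ANCOVA contrasts is valid but stricter than three arms require; a closed test or Holm gains power with no added patients

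*Combined protocol and SAP*

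**What the plan says.** Section A, aim 2, is to "Compare 3D RV EF between SAVR, mini AVR, TAVR", and Section D gives "Primary outcome: 3D RV EF". There are three arms and therefore three pairwise contrasts.

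Section E, Statistical analysis, names ANCOVA for the RV indices with "pos-hoc pairwise comparisons with Bonferroni correction", and adds: "Statistical significance is set at $p < 0.05". It lists five ANCOVA covariates, and lists them only for percentage change from Timing #1 to Timing #3. A Mann-Whitney U test is the option for two groups. No closed or stepwise procedure is named, and the text does not say whether the pairs are tested only after a significant global arm effect.

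Section E, Power analysis, sizes the trial on one two-group comparison, SAVR against TAVR, of percentage change in RV strain (-25.2 against -20.0), with the "criterion for significance (alpha) set at 0.05 and 80% power". It concludes: "we obtained a sample size of 22 patients per group". The alpha used there is not divided by three, and no SD is given.

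**The concern.** Bonferroni guards against all three pairwise nulls failing separately. With three arms that pattern is constrained: if two of the pairwise equalities hold, so does the third. A method that uses this fact can test each pair at 0.05 after a significant global test and still keep the family-wise error at 5%. Bonferroni does not use it and gives up power.

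This matters because 22 per group was chosen for a single comparison at 0.05. Dividing alpha by three lowers the power of one such Mann-Whitney contrast from 80% to about 65%, on the back-solved effect. Part of that loss can be recovered without enrolling anyone else.

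**Working it through.** **Inputs.** Three arms of 22, 66 in all (Section E; equal allocation assumed). Five covariates, so residual df = 66 - 3 - 5 = 58. Alpha 0.05, taken as two-sided because sidedness is not stated. Difference 25.2 - 20.0 = 5.2 points.

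**The plan's own figure.** Without an SD, 22 per group cannot be reproduced independently. Working backwards with a two-sample t formula and Mann-Whitney efficiency 3/pi, 22 per group at 80% power implies an SD of about 5.87, so d = 5.2/5.87 = 0.886. Other test variants (one-sided, no efficiency factor, worst-case efficiency) give SDs from 5.57 to 6.82, so d runs from 5.2/6.82 = 0.76 to 5.2/5.57 = 0.93.

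**Cost of Bonferroni in patients.** The sample size ratio is (2.394 + 0.842)^2 / (1.960 + 0.842)^2 = 10.47/7.85 = 1.33. 22 x 1.33 = 29.3, so about 30 per group would restore 80% for one contrast.

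**Why the closed test is valid.** There are three cases.
- All arms equal: any false claim needs the global test to reject, which has probability 5%.
- Exactly one pair equal: only that pair can be falsely claimed, and it is tested at 5%. Bonferroni tests it at 1.67%.
- All arms different: no false claim is possible.

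Exactly two equal pairs cannot occur. The argument does not depend on effect size, and it is special to three arms.

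**Simulation of the ANCOVA** (3 x 22, five covariates, 58 df, pooled variance, d about 0.89; 40,000 runs per scenario, with separate repeat runs agreeing to about one point):

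| Quantity | Bonferroni | Holm | Closed |
|---|---|---|---|
| Family-wise error, all arms equal | 4.3-4.4% | - | 5.0-5.1% |
| Family-wise error, one pair equal | 1.5-1.8% | - | 5.1% |
| Power SAVR-TAVR, mini AVR midway | 64% | 65% | 68% |
| Power SAVR-TAVR, mini AVR equal to another arm | 64% | 67% | 74% |
| Power, each adjacent mini AVR contrast, midway | 16% | 20% | 27% |

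The simulation standard error at 5% is sqrt(0.05 x 0.95/40,000) = 0.11 points, so 5.1% is consistent with 5%. When mini AVR equals SAVR, power to detect both true differences rises from 48% to 67%.

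**Sensitivity to the assumed effect.** A normal approximation for one contrast without covariates uses lambda = d x sqrt(22/2), with power = Phi(lambda - 1.960) unadjusted and Phi(lambda - 2.394) under Bonferroni.
- d = 0.76: lambda 2.53, 72% against 55%.
- d = 0.886: lambda 2.94, 84% against 71%.
- d = 0.93: lambda 3.10, 87% against 76%.

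These levels are higher than the simulated ones because the approximation ignores the covariates and the estimated variance. The gap, roughly 11 to 16 points, limits what the closed test can gain on one contrast, so the point does not depend on the exact SD.

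**Unequal variances.** With pooled variance, and the two equal arms at 1.5 or 2 times the SD of the third, the closed test's family-wise error was about 7% and 8 to 9%. Bonferroni's was about 3% and 3.5 to 4%. With unequal group sizes as well, the figures were 10% and 4.5%.

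**The case against.** The strongest reply is that nothing here is wrong. Bonferroni is valid and simple, and its slack gives some protection. That protection is real: the outcome is a percentage change compared across three different procedures, the documents give no assurance of equal variance, and the pooled closed test can exceed 5% where Bonferroni does not. This part stands, and it is why the replacement needs unequal-variance standard errors. The fault in that setting lies in the pooled standard error rather than in the closure: Holm inflates equally there when the third arm is far away. Without covariates, and with SDs in ratio 2, a Welch global test with Welch pairs held 4.9%; with equal SDs it kept the gain (67% to 77% when mini AVR equals another arm).

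Other limits also stand. The effect is back-solved for RV strain, whereas the primary outcome is 3D RV EF. The power figures in the table use pooled variance; a conservative small-sample robust correction could absorb much of the 4-point gain in the midway case. Adjacent mini AVR contrasts remain weak at about 27%. The gated test loses a rejection that ungated Bonferroni would make in about 0.1-0.5% of data sets. If the planned pairwise tests already wait for a significant global test, it never loses one.

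A reader might infer that the closed test carries the same guarantee under all conditions, applies to every index and time point, or brings power back to 80%. The documents support none of these. The first needs equal variances or robust errors. On the second, Section E states the ANCOVA covariates only for change from Timing #1 to #3 and also plans Mann-Whitney tests, which a global-then-pairs ANCOVA rule does not cover. On the third, the best simulated level for a single contrast with the planned covariates is 74%.

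The objection that this is only preference does not dispose of the point. Holm rejects everything Bonferroni rejects, relies on the same validity of the p-values, and costs only matching confidence intervals.

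**Conclusion.** The point holds as a cheap improvement and not as an error in the plan. For the ANCOVA of percentage change from Timing #1 to #3, within one index, the closed test raises power by about 4 points for SAVR-TAVR with mini AVR midway, 10 points when mini AVR equals another arm, and 11 points for adjacent mini AVR contrasts. Holm gains about 1, 3 and 4 points.

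The sizes rest on 22 per arm, pooled variance and an assumed effect of about 0.89 SD (range 0.76 to 0.93). The error-control argument does not rest on the effect, but it does need standard errors that remain valid if the arms differ in variance. Control is within each index; neither Bonferroni over three pairs nor the closed test covers 3D RV EF, RVFAC and TAPSE jointly.

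**What to change.** In Section E, Statistical analysis, replace the Bonferroni wording for this ANCOVA with:

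> For the ANCOVA of percentage change from Timing #1 to Timing #3, within each RV index: if the global arm effect is significant at 0.05, each of the three pairwise contrasts is tested at 0.05 (closed procedure for three groups); otherwise no pairwise claim is made. The global and pairwise tests use unequal-variance (robust) standard errors.

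Name the robust estimator, and settle the wording before the data are analysed. If a rule based only on p-values is preferred, replace Bonferroni with Holm.

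The cost is two sentences of SAP text and no patients. Ordinary 95% confidence intervals will not match the tests exactly and must be labelled as unadjusted. The Mann-Whitney comparisons need their own multiplicity statement if they are to support pairwise claims.

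### The ANCOVA of change in RV indices adjusts for vasopressor dose at T3, after the procedure, so its arm contrast need not be the procedure difference that Aim 2 asks for

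*Combined protocol and SAP*

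**What the plan says.** All references are to the combined protocol and SAP.

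- **Aim.** Section A, Aim 2: "Compare 3D RV EF between SAVR, mini AVR, TAVR". Section D: "Primary outcome: 3D RV EF".
- **Response.** Section E, Statistical analysis: "For ANCOVA of % change (Timing #3 from #1) in RV indices".
- **Covariates.** Same paragraph: "covariates included age, gender, norepinephrine equivalent (NE equiv) at Timing #3, CVP at Timing #1", together with the T1 value of the index being analysed. No other covariate set is given for this ANCOVA, and no reason is given for including NE equivalent at T3.
- **When T3 is.** The timing table under Aim 2 defines it as "Post chest closure or before extubation".
- **How dose is set.** Section D, Anesthesia methods: "Choice of the medication including inotropes and vasopressors, and intervention such as transfusion and fluid management will be at each anesthesiologist's discretion".

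No estimand is stated. Section E also names a Mann-Whitney U test for two-group comparisons of the RV indices, joined to the ANCOVA by 'or', and does not say which is the main analysis.

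**The concern.** Age, gender, CVP at T1 and the index at T1 are all fixed before the valve procedure. NE equivalent at T3 is not. It cannot have influenced which procedure the patient had, so it is not a baseline confounder.

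It may, however, be a consequence of the procedure (two arms go through CPB, TAVR does not), of the RV response, or of both. Conditioning on a consequence of the exposure changes the question. The contrast then compares patients who ended up on the same vasopressor dose, rather than patients who had different procedures. If dose also reacts to RV function, the adjustment can create an arm difference by itself.

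At stake is the three-arm comparison of the primary outcome, for which the ANCOVA is the only method in section E that takes more than two groups.

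**Working it through.** **1. Timing of each model term**

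| Term | Measured | Relative to procedure |
|---|---|---|
| Age, gender | baseline | before |
| CVP, RV index | T1, post induction | before |
| NE equivalent | T3 | after |
| Response (change T1 to T3) | T3 | after |

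This step needs no assumption.

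**2. The plan's own figure, used only to set a scale.** Section E gives 22 per group from RV strain changes of -25.2 and -20.0 (difference 5.2), alpha 0.05 and 80% power, Mann-Whitney, with no SD. Assuming SD 6, two-sided testing and relative efficiency 0.955:

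n = 2 × (1.960 + 0.842)² × 6² / 5.2² = 20.9, rounded up to 21; 21 / 0.955 = 21.99, so 22.

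Other readings (one-sided, or efficiency 0.864) imply SDs between about 5.6 and 6.8. The 22 can therefore be neither confirmed nor refuted. It concerns RV strain, not 3D RV EF. SD 6 is an illustration below, and the point does not depend on it.

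**3. General identity.** Adjusted contrast = unadjusted contrast - (within-arm slope of response on NE) × (arm difference in NE). In within-arm SDs, assumed inputs give these shifts:

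- NE difference 0.5, slope -0.2: +0.10
- NE difference 1, slope -0.3: +0.30
- NE difference 2, slope -0.4: +0.80
- either input zero: 0
- a positive slope reverses the sign.

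**4. A simple causal model (every parameter assumed).** Let τ be the procedure effect on RV change not passing through NE, SAVR minus TAVR. Let NE = a·arm - c·(RV change/6) + noise of SD 1, and response = RV change + b·NE. Then:

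- total effect = τ + b(a - cτ/6)
- NE-adjusted estimate = (τ + 6ac) / (1 + c²)

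| τ | a | c | b | Total effect | NE-adjusted |
|---|---|---|---|---|---|
| -5.2 | 1 | 0 | 0 | -5.2 | -5.2 |
| -5.2 | 0 | 0.3 | 0 | -5.2 | -5.2/1.09 = -4.8 |
| -5.2 | 0.5 | 0.5 | 0 | -5.2 | (-5.2 + 1.5)/1.25 = -3.0 |
| -5.2 | 1 | 0.5 | 0 | -5.2 | (-5.2 + 3.0)/1.25 = -1.8 |
| -5.2 | 1 | 0.8 | 0 | -5.2 | (-5.2 + 4.8)/1.64 = -0.2 |
| -5.2 | 1 | 0 | 1 | -4.2 | -5.2 |
| 0 | 0.5 | 0.5 | 0 | 0 | 1.5/1.25 = +1.2 |
| 0 | 1 | 0.5 | 0 | 0 | 3.0/1.25 = +2.4 |

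A simulation of 400,000 patients per case agreed with these values. The rows show no shift, shifts toward zero, one shift away from zero, and two spurious differences.

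**5. Error rates in the same model.** These come from 5,000 simulated two-arm trials of 22 per arm, two-sided 0.05, b = 0 and c = 0.5. With a = 0.5 or a = 1, rejection when the total effect is zero is about 5% without NE, and 11% or 27% with it. Power for -5.2 falls from about 80% to 36% or 15%.

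**6. Precision.** With 22 in each of three arms (66 - 3 = 63 df, other covariates ignored), the variance ratio for a pairwise contrast is (1 + 22δ²/(2 × 63)) × (1 - r²) × 63/62. Here δ is the NE difference in SDs and r the within-arm correlation.

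- δ = 1, r = 0.3: 1.175 × 0.91 × 1.016 = 1.09
- δ = 2, r = 0.4: 1.698 × 0.84 × 1.016 = 1.45
- δ = 1, r = 0.5: 1.175 × 0.75 × 1.016 = 0.90

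The interval may widen or narrow.

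**The case against.** The strongest defence is that vasoactive support at imaging affects what the echocardiogram shows, and that the investigators want arms compared at equal support. That is a legitimate question, but it is a direct-effect estimand. The plan neither states nor justifies it, and the adjusted estimate is still biased for it if dose responds to RV function (c above zero in the model).

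Three further objections stand and limit the point:

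- **The causal structure is inferred.** Section D says dosing is discretionary; it does not say that dose follows the procedure or RV function. Both are plausible, and section B expects RV function to fall more after SAVR than TAVR, but no NE data are given.
- **The ANCOVA is not designated as the primary analysis.** The Mann-Whitney test is an unadjusted alternative, although 'or' leaves its use open and it handles two groups only.
- **Omitting NE does not yield the causal effect of the procedure.** No randomisation is described, so choice of procedure remains a source of confounding.

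A reader might infer that the adjustment must hide part of a real SAVR-TAVR difference, or that it must widen the interval. The documents support neither: the shift can be zero or of either sign, and so can the change in precision.

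**Conclusion.** The point holds as a defect of specification. The only ANCOVA covariate set contains a post-procedure variable concurrent with the outcome, without an estimand, a justification or an ANCOVA that omits it. That rests on the text alone.

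That the contrast is actually distorted rests on an assumption: that dose depends on the procedure or on the RV response in a way that also links it to the index. If dose neither responds to RV change nor affects the index, there is no bias. Otherwise the adjusted contrast may be pulled toward zero, pushed away from it, or made non-zero when there is no difference. The size and direction for this trial cannot be computed from the documents. The figures above show what assumed values would do on an assumed SD of 6, and they should not be read across to 3D RV EF.

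**What to change.** In section E:

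1. Name the main ANCOVA and restrict its covariates to pre-procedure variables: age, gender, CVP at T1 and the index at T1.
2. Report NE equivalent at T3 by arm as a descriptive result.
3. Keep the T3-adjusted model only as a labelled sensitivity analysis, stating that it targets a comparison at equal vasoactive support and what it assumes.
4. State that the arms are not described as randomised and that confounding by choice of procedure remains.

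The cost is analysis wording; no patients or measurements are added or lost. Section E describes the covariates in the past tense, so if the adjusted model has already been run, the change should be disclosed as made afterwards and both results shown. The one small loss is that the main model no longer accounts for vasoactive support at imaging, which the sensitivity analysis still shows.

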4. Risks and assess likelihood and seriousness. No research related risks are anticipated because TEE measurements are standard care
5. Procedures for protecting against or minimizing potential risks. N/A
6. Potential benefits and importance to the subjects and others. Patients may benefit from more detailed clinical data than usual by joining this study. Especially, training cardiac anesthesiologists for 3D TEE will help for obtaining more clinical data which might be leading to necessary intervention.
7. Why risks are reasonable in relation to benefits. No research related risks are anticipated, and possible benefits are higher (described in 6)

H. Data and Safety Monitoring Plan

All protocols that pose greater than minimal risk must have a Data and Safety Monitoring Plan (see DHSP policy G 616 "Independent Monitoring of Investigator-Initiated Clinical Trials.")

1. Describe the Data and Safety Monitoring Plan (DSMP)
We will report to IRB if we should come across research related complications

2. If applicable, describe the Data and Safety Monitoring Board (DSMB) that will be responsible for monitoring the study. Indicate Chair, members, areas of expertise, frequency of meetings, distribution of reports.

N/A

I. Literature Cited

1. Lang RM, Badano LP, Mor-Avi V, Afilalo J, Armstrong A, Ernande L,

et al. Recommendations for cardiac chamber quantification by echocardiography in adults: an update from the American Society of Echocardiography and the European Association of Cardiovascular Imaging. J Am Soc Echocardiogr 2015;28(January (1)). 1–39.e14.

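### The arms are not described as randomised and the ANCOVA adjusts for no preoperative surgical-risk or severity measure, so the SAVR, mini AVR and TAVR comparisons are open to confounding by indication

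*Combined protocol and SAP*

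**What the plan says.** Section D gives the design as "Prospective clinical trial at single-center tertiary academic hospital" and lists the three procedures as arms. The readable text mentions no randomisation, matching, weighting or propensity method. Aim 2 in section A is "Compare 3D RV EF between SAVR, mini AVR, TAVR".

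Three statements bear on how patients reach an arm:

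- Section G, item 4: "No research related risks are anticipated because TEE measurements are standard care". Only the imaging is considered as a research risk; the valve procedure is not.
- Section G, item 3: consent is taken by telephone before surgery, or "actual consent will be obtained in preoperative holding area".
- Section G, item 1: "Exclusion criteria: patients' refusal, suboptimal echocardiography data". Eligibility sets no limit on surgical risk, ventricular function, valve severity or comorbidity.

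In section E, the ANCOVA of percentage change from T1 to T3 has five covariates: "covariates included age, gender, norepinephrine equivalent (NE equiv) at Timing #3, CVP at Timing #1", "and each RV index at the baseline (Timing #1". Pairwise comparisons follow with Bonferroni correction. The alternative for two groups is a Mann–Whitney U test, which adjusts for nothing. Section G, item 2 names the data sources: "Echocardiography data, medical information in EPIC".

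**The concern.** If clinicians choose the procedure, patients in the three arms may differ before surgery in ways that also affect how the right ventricle responds. The covariate list is the plan's only protection. It includes nothing that summarises surgical risk, left ventricular function, valve severity, pulmonary pressure or comorbidity.

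One of the five places goes to norepinephrine equivalent at T3. This is measured after the intervention and may lie on the path from procedure to RV function, so it cannot stand in for baseline risk.

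At stake is Aim 2. A difference between patient groups could appear as a difference between procedures, or could cancel one. The plan does not mention confounding and does not limit the arm differences to associations.

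**Working it through.** **Inputs from the documents.** 22 patients per group, so 66 in three arms; alpha 0.05; 80% power for a Mann–Whitney U test; RV strain changes of -25.2 (SAVR) and -20.0 (TAVR), a difference of 5.2 points.

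**Assumptions.** Two-sided testing; three pairwise contrasts; a preoperative risk factor whose arm means differ by D standard deviations, given the listed covariates; a correlation r between that factor and the change in RV index, beyond the listed covariates. The documents give neither D nor r.

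**1. The plan's own figure.** No SD is stated, so 22 per group cannot be reproduced from 5.2 points. Working backwards, a Mann–Whitney test with efficiency 3/π relative to the t-test has 22 × 3/π = 21.0 effective patients per group. The effect detectable with 80% power is then 0.886 SD, which implies an SD of 5.2/0.886 = 5.87 points.

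**2. Bias.** Bias in SD units = D × r. With D = 1 and r = 0.2, 0.3, 0.4, it is 0.2, 0.3, 0.4 SD. Against 0.886 SD that is 23%, 34% and 45% of the effect the study is sized to detect.

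**3. False positives when the procedures do not differ.** The standard error in SD units is √(2/22) = 0.3015, so the noncentrality is bias/0.3015. Degrees of freedom are taken as 66 - 3 = 63; the loss from the covariates is ignored. The Bonferroni level is 0.05/3 = 0.0167. Two-sided critical values are 1.998 at 0.05 and 2.460 at 0.0167.

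| Bias (SD) | Noncentrality | p < 0.05 | p < 0.0167 |
|---|---|---|---|
| 0 | 0 | 5.0% | 1.67% |
| 0.2 | 0.663 | 10.0% | 4.2% |
| 0.3 | 0.995 | 16.5% | 7.8% |
| 0.4 | 1.327 | 25.7% | 13.6% |

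The last column matches the planned pairwise comparisons: about 2.5 to 8 times the nominal rate.

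**4. Bias against a true difference.** With a true effect of 0.886 SD, the noncentrality is 0.886/0.3015 = 2.939 and power at 0.0167 is 68%. A bias of 0.2, 0.3 or 0.4 SD in the opposite direction leaves 0.686, 0.586 or 0.486 SD, and power falls to 43%, 31% or 21%.

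**5. When it hardly matters.** With D = 0.25 and r = 0.2 the bias is 0.05 SD, and the false-positive rate at an unadjusted 0.05 is 5.3%.

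**6. Precision cost of adjusting for the score.** Variance ratio = [(2/22 + D²/63)/(2/22)] × (1 - r²). The bracket is 1.175 for D = 1 and 1.393 for D = 1.5.

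| r | D = 1 | D = 1.5 |
|---|---|---|
| 0 | +17% | +39% |
| 0.2 | +13% | +34% |
| 0.3 | +7% | +27% |
| 0.4 | -1% | +17% |

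**The case against.** **The list already controls part of this.** Age, CVP at T1 and the baseline RV index bear on risk and right-heart status. That stands, and it is why the illustration uses only imbalance and correlation left over after them. But T1 follows induction, so CVP and the index are not preoperative values, and none of the three covers surgical risk, valve severity, left ventricular function or comorbidity.

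**The size is assumed throughout.** This stands too. With a small imbalance the effect is negligible (step 5).

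**A swap is not free.** It keeps the number of covariates at five, but a covariate that is unbalanced between arms costs precision (step 6), in a study with no stated allowance in its sample size. Removing norepinephrine equivalent also changes what is estimated, because vasopressor choice is left to the anesthesiologist. Both points stand. They argue for keeping the present model as a sensitivity analysis, not for leaving baseline risk out.

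**Stronger readings that the documents do not support.** A reader might infer that the comparison is confounded, or that selection will favour one procedure. The text never states how arms are assigned, and a figure in the design section is not shown. Clinical selection is an inference from the absence of any allocation text, the standard-care framing and the timing of consent. A reader might also take the 10% to 26% column as the plan's error rate, but that ignores the Bonferroni step. Nor would one score necessarily restore the nominal rate: it does so only if the score carries all the omitted confounding.

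**Conclusion.** The point holds as a gap in the analysis plan. As written, all three arm contrasts are open to confounding by indication, most plainly in the unadjusted Mann–Whitney alternative, and direction and size cannot be learned from the documents. If residual imbalance is 1 SD and the correlation 0.2 to 0.4, the bias is a quarter to nearly a half of the detectable effect. It can produce false positives above the 1.67% level or hide a real difference. Bonferroni correction lowers the false-positive rate but does not remove bias from the estimate. The p-values mislead only if read as tests of a procedure effect; as tests of an adjusted association they are not invalidated by this. The change should be made.

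**What to change.** In section E:

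- In the primary ANCOVA, replace norepinephrine equivalent at T3 with one preoperative summary of surgical risk, abstracted from the medical record and defined identically in all three arms. Keep age, gender, CVP at T1 and the baseline RV index.
- Report the model with norepinephrine equivalent at T3 as a sensitivity analysis.

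In section D, state how patients come to be in each arm and, if it is so, that arms are not randomised. State that differences between arms are adjusted associations.

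**Cost.** A few sentences and one abstracted variable. The record is already a study data source, but the documents do not confirm that a suitable summary is available in every arm, so this should be checked before the wording is fixed. Contrast variance changes by about -1% to +17% at a 1 SD imbalance and by +17% to +39% at 1.5 SD. One score reduces confounding but may not remove it, so the statement about associations is needed even with the new covariate.
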